## **5. Inclusion/Exclusion Criteria**

Subjects will be recruited from patients who have presented to Otolaryngology clinics with complaints of nasal obstruction. Specifically, patients who have been found to have nasal valve collapse by an Otolaryngologist based on performance of the Cottle maneuver will be invited to participate in the study. Additionally, participants will be evaluated for inclusion in the same manner if they were recruited utilizing flyers, social media, or discovered our study via the clinicaltrials.gov website. They will be excluded if after examination they are determined by their Otolaryngologist to be unsuitable or unsafe for an internal nasal dilator (e.g. history of granulomatosis with polyangiitis, extensive prior sinus or turbinate surgery altering nasal cavity anatomy, pre-existing mucosal injuries or abnormalities). Included participants will then be asked to complete the survey, NOSE questionnaire, and testing session either at the same visit or on another visit depending on patient and tester availability. Additionally we will include a control arm whom do not have evidence of nasal valve collapse, but are willing to participate in the study. Members of the control arm will also be excluded if they are deemed unsuitable based on nasal anatomy and/or the above exclusion criteria listed above.

## **6. Drugs/ Substances/ Devices**

*a. The rationale for choosing the drug and dose or for choosing the device to be used.*

The control devices (Breathe Right strips, Sleep Right dilator, Mute dilator, Nozovent dilator, and Max Air nose cones) were selected from several other nasal obstruction products available on the market based on discussions with patients and opinion leaders in nasal airway obstruction due to their popularity and reported effectiveness. These are all legally marketed in the United States as Class I 510(k) exempt medical devices available over-the-counter.

The Schnozzle was developed as a non-invasive, discreet alternative to the current products available for nasal airway obstruction. Schnozzle is still in prototype form, and this testing will influence final design updates to improve the dilator before full-scale manufacturing and marketing. For this testing, Schnozzle prototypes will be produced using an FDA approved silicone.

Schnozzle is a Class I device not requiring FDA approval prior to use in humans. It fits into the existing internal nasal dilator classification as defined by Code of Federal Regulations (CFR) Title 21, Part 874 - Ear, Nose, Throat Devices, Subpart D - prosthetic devices, section 874.3900. According to this definition, a nasal dilator “provides relief from temporary causes of breathing difficulties resulting from structural abnormalities” through a mechanism that “decreases airway resistance and increases nasal airflow”. More specifically, the Schnozzle device fits into the internal nasal dilator subcategory. As stated in the FDA’s ruling, “the internal nasal dilator is constructed from metal or plastic and is placed inside the nostrils; it acts by pushing the nostrils open or by gently pressing on the columella”. The Schnozzle nasal dilator fits this definition, being a prosthetic device placed inside the nostril with the purpose of increasing nasal airflow.

As confirmed by Greenleaf Health, a regulatory consulting firm, Schnozzle can be considered Class I device exempt from 510(K) premarket notification.

- b. Justification and safety information if FDA approved drugs will be administered for non-FDA approved indications or if doses or routes of administration or participant populations are changed.* N/A
- c. Justification and safety information if non-FDA approved drugs without an IND will be administered.* N/A

Date: 7/6/20

Principal Investigator: [name]

Application Number: IRB00135539

## 7. Study Statistics

### a. Primary outcome variable.

Peak Nasal Inspiratory Flow (PNIF) and Nasal Obstruction Symptom Examination (NOSE) score for each individual before the trial and while using each tested nasal dilator.

### b. Secondary outcome variables.

Comfort, appearance, ease of use, and general favorability of each device.

### c. Statistical plan including sample size justification and interim data analysis.

The purpose of this pilot study is to understand patient needs and preferences regarding nasal dilators, and to use this data to refine the design before potentially marketing the product. In this pilot study we plan to test 70 individuals with nasal valve collapse. Previous studies have demonstrated an ability to detect a statistically significant difference in PNIF with a power of 80% and an alpha of 0.05 with a sample size of 30 patients with nasal valve collapse. We aim to recruit 70 individuals, 35 patients with nasal valve collapse, 35 patients without nasal valve collapse with expected attrition of 5 patients in each cohort.[12] If we proceed to pursue statistical evaluation of the data we will use ANOVA with a  $p < 0.05$  predetermined as significant.

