#### **4. Study Procedures**

##### *a. Study design, including the sequence and timing of study procedures (distinguish research procedures from those that are part of routine care).*

###### **Recruitment:**

Participants will be recruited from patients presenting to Otolaryngology clinics with symptoms of nasal obstruction. The otolaryngologist in clinic will screen these patients for nasal valve collapse as they would in standard clinical practice. This involves visualizing the nasal cavity through nasal endoscopy and testing the nasal valve using Cottle maneuver (applying lateral force to the cheek to open the nasal valve) or the modified Cottle maneuver (using a cotton tip applicator to open the nasal valve from inside the nasal cavity) and evaluating for improvement in nasal obstruction symptoms. Improved nasal airflow during the maneuver suggests nasal valve collapse contributes to restricted nasal airflow.

The clinical Otolaryngologist will counsel patients with nasal valve collapse regarding the various treatment options as they would in routine clinical practice (management options include to doing nothing, using existing nasal dilator devices, or undergoing surgery). Patients will then be invited to participate in the study, which would involve a study session in which they are fitted with six nasal dilator devices, instructed in proper care and use, and report on their function and comfort. Additional participants will be recruited from patients who present to Otolaryngology clinics with symptoms unrelated to nasal breathing to serve as a control group. Participants will also be recruited via the clinicaltrials.gov website, as well as using recruitment flyers and social medial posts.

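### Section 7c gives two incompatible numbers of patients with nasal valve collapse, 70 and 35; only 35 fits the rest of the plan

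*Combined protocol and SAP*

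**What the plan says.** The planned numbers appear in one paragraph, section 7c (statistical plan and sample size justification). It makes three statements in this order:

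- The number to be tested: "In this pilot study we plan to test 70 individuals with nasal valve collapse".
- The basis for the size, taken from earlier work on PNIF: 80% power at an alpha of 0.05, "with a sample size of 30 patients with nasal valve collapse".
- The recruitment target: "We aim to recruit 70 individuals, 35 patients with nasal valve collapse, 35 patients without nasal valve collapse with expected attrition of 5 patients". The sentence goes on to apply that loss of 5 to each cohort.

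Two other sections describe the cohort without collapse but give no number for it. Section 4a (Recruitment) adds "patients who present to Otolaryngology clinics with symptoms unrelated to nasal breathing to serve as a control group". Section 5 (Inclusion/Exclusion Criteria) says "we will include a control arm whom do not have evidence of nasal valve collapse". The only other participant counts are in section 7d, which sets data reviews after 5 and after 10 participants. Those counts are not split by cohort and say nothing about the final size.

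**The concern.** The first and third statements use the same figure, 70, for different things. In the first, 70 is the number of patients with nasal valve collapse. In the third, it is the total over two cohorts, half of whom do not have collapse.

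What is at stake is the recruitment target for the cohort in which the device is meant to work. A reader who takes the first sentence at face value expects twice as many patients with collapse as the recruitment sentence provides. That reader would judge a fully recruited collapse cohort of 35 to be half complete. No other section states a cohort size, so the conflict cannot be settled by looking up the number elsewhere. It has to be worked out from the attrition allowance and from the descriptions of the control cohort.

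**Working it through.** **Inputs, all from section 7c**

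- Completers with collapse in the power sentence: 30
- Expected attrition: 5 per cohort
- Recruitment target: 35 with collapse, 35 without, 70 in total
- First sentence: 70 with collapse

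**Step 1. Reproduce the plan's total.**
Recruited per cohort = completers + attrition = 30 + 5 = 35.
Total = 2 × 35 = 70.
As a rate, attrition is 5/35 = 14.3%, and 30 / (1 − 5/35) = 35.
The recruitment sentence reproduces exactly, and 70 is the total over both cohorts.

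**Step 2. Compare the two counts of patients with collapse.**
First sentence: 70. Recruitment sentence: 35.
Ratio = 70/35 = 2.

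**Step 3. Check whether both sentences can hold.**
With a total of 70 and 70 of them having collapse, the number without collapse is 70 − 70 = 0. The recruitment sentence says 35. The two are incompatible.

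**Step 4. Ask which sentence agrees with the other sections.**
Sections 4a and 5 both provide for participants without collapse. That fits 35 and 35 and does not fit a sample made up entirely of patients with collapse.

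**Step 5. Expected completers under the 35/35 split.**
With collapse: 35 − 5 = 30, which is the number in the power sentence.
Without collapse: 35 − 5 = 30.
Both cohorts: 30 + 30 = 60.

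**Step 6. Look for anything that depends on the first sentence.**
The power sentence uses 30, the attrition allowance is set per cohort of 35, and the reviews in section 7d use 5 and 10. None of these is derived from 70 patients with collapse.

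**The case against.** The strongest reply is that this is a slip in wording which the paragraph corrects itself. Two sentences later it gives the total, the split and the attrition, and these lead back to the 30 in the power sentence. No figure rests on the mistaken count, and a careful reader will reach 35 and 35. Most of this stands, and it is why the point is moderate and not more serious. It does not remove the need for the edit. The wrong count is the opening statement of sample size in the section that exists to justify it, and no other section gives a cohort size to check it against.

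It could also be argued that the split is the faulty sentence. Section 4e treats each participant's baseline without a device as the non-treatment arm, so a design with collapse patients only would be conceivable. But sections 4a and 5 explicitly bring in separate participants without collapse, and 30 + 5 per cohort leads to 35, not 70. The evidence favours the split, though only the investigators can confirm it.

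A reader might infer more: that the collapse cohort is only half the size it needs to be, or that the stated power is invalid. The documents do not support either. The power sentence is tied to 30 patients with collapse, and the 35/35 split delivers 30 after attrition. The documents give no PNIF difference or standard deviation, so the 80% can be neither confirmed nor refuted from them. The contradiction in head count has no bearing on it.

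**Conclusion.** The point holds as an internal contradiction in section 7c. The number of patients with nasal valve collapse is 70 in one sentence and 35 in another. The second fits the attrition arithmetic and the control cohort in sections 4a and 5, so the first overstates the collapse cohort twofold. The intended plan appears to be 70 recruited, 35 in each cohort, with 30 completers expected in each and 60 overall.

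Severity is moderate: a stated sample size is wrong as written, but no calculation changes. The conclusion assumes that the attrition of 5 applies to each cohort, as the text says, and that the control cohort is a current part of the design, as sections 4a and 5 indicate. It makes no claim about the adequacy of the sample size or the power.

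**What to change.** The investigators should confirm that 35 with and 35 without collapse is the intended split. If so, replace the first sample size sentence in section 7c with wording such as: *The pilot will test 70 participants in total, 35 with nasal valve collapse and 35 without; 30 are expected to complete in each cohort.* The power and recruitment sentences can stay as they are for this purpose.

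The cost is one sentence and one confirmation. Enrolment, procedures and analysis do not change. If the investigators instead intended 70 patients with collapse, the recruitment sentence and the attrition allowance would have to be rewritten and reconciled with sections 4a and 5, which is a larger change.

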### 2. Objectives (include all primary and secondary objectives)

#### *Primary objective:*

Determine the effectiveness of the Schnozzle nasal dilator compared to existing nasal dilator products and a control (unaided breathing) using objective peak nasal airflow (PNIF) measurements and the Nasal Obstruction Symptom Evaluation (NOSE) instrument.

*Secondary objective:*

Determine the comfort, inconspicuousness, usability, overall patient satisfaction, device compliance, sizing, pricing, and other patient perception of the nasal dilator products.

**3. Background** (*briefly describe pre-clinical and clinical data, current experience with procedures, drug or device, and any other relevant information to justify the research*)

Mechanical nasal obstruction is one of the most common complaints heard by otolaryngologists every day [3]. In fact, over 73% of the population experiences continually elevated inspiratory resistance as a result of obstructed nasal airflow [4]. In patients seeking treatment, the primary causes of nasal obstruction are chronic inflammation due to allergies (38%) and permanent structural abnormalities (62%) [9]. While the inflammatory causes of nasal obstruction are generally well controlled with topical and systemic pharmacotherapy, the structural impediments to airflow must be treated through mechanical alteration of these flow-limiting segments [10].

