###### **Study design:**

If a patient expresses interest in participating they will be introduced to a member of the research team to discuss the study and complete informed consent. All participation is voluntary and participants are able to withdraw from the study at any point. The study participant will be asked to complete a questionnaire, which was adapted from the previously approved survey ([IRB00122933](#)), which includes the NOSE instrument, questions regarding the patient's current treatments, and a ranking of their preferred characteristics of an ideal nasal dilator (see Appendix A).

Patients will then be asked to inhale rapidly into an airflow transducer to measure baseline peak nasal inspiratory flow (PNIF). Following the pre-test survey participants will be fitted serially with five commercially available nasal dilator products per manufacturer recommendations (Breathe Right strips, Max Air nose cones, Sleep Right dilator, Mute dilator, and Nozovent dilator), and one experimental nasal dilator designed by the research team ("Schnozzle"). In this crossover design study participants will be blinded as to which dilators are branded and which are experimental, and the order of fitting nasal dilators will be randomized. Each subject will undergo PNIF testing for all six devices.

After each fitting and use for five minutes to adjust to the device and confirm there is no immediate discomfort or irritation, participants will undergo repeat PNIF testing with each device and then will be free to go home and trial the devices on their own. Participants will be given a schedule specifying one device to trial for at least one continuous hour per day. This schedule will specify devices in a randomized order,

and participants will continue to be blinded as to which device they will be using on a particular day (Schnozzle, Breathe Right, Max Air, Sleep Right, Mute, and Nozovent). The devices will be numbered in a random fashion, for participants to be able to identify which device via the assigned number they are scheduled to use on that day. They will similarly use the device number when performing any device evaluation.

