*c. Blinding, including justification for blinding or not blinding the trial, if applicable.*

Patients will be blinded to the names of the devices tested to limit bias when they complete the surveys. They will also be blinded as to which device was designed by members of the research team.

*d. Justification of why participants will not receive routine care or will have current therapy stopped.*

The standard of care is to do nothing, use existing nasal dilator devices, or surgery. This one session comparison study of nasal dilators does not prevent patients from proceeding with the standard of care after the study session, and will familiarize them more thoroughly with available treatment options.

*e. Justification for inclusion of a placebo or non-treatment group.*

Participants will serially wear the prototype Schnozzle device and marketed nasal dilators, all of which are treatments. We will get a baseline NOSE and PNIF score from participants without any assistive devices in place, which serves as the placebo/ non-treatment arm of the study. Following the study session participants can continue to use currently marketed nasal dilators or proceed with planning surgery.

*f. Definition of treatment failure or participant removal criteria.*

Participants will be removed from the study if they experience substantial discomfort with the study devices, or if they experience any adverse events, such as epistaxis, or skin breakdown or if they would like to discontinue testing for any reason.

*g. Description of what happens to participants receiving therapy when study ends or if a participant's participation in the study ends prematurely.*

At the end of the study session participants will be able to continue using any of the marketed nasal dilator products currently on the market, and this study will not influence their ability to proceed with scheduling surgery if indicated and desired. They will not be able to continue using the Schnozzle nasal dilators at this time as it is still in early stage development and not widely produced or available.

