## **9. Benefits**

*a. Description of the probable benefits for the participant and for society.*

By participating in this study, individuals with nasal valve collapse will have an opportunity to trial several existing nasal dilators. In typical clinical practice patients are given recommendations for several types of nasal dilators but are not fitted and trained in appropriate use. Participants may notice a marked improvement in their ability to breathe while wearing the devices and an enhancement in quality of life.

Schnozzle has the potential to improve of the quality of life for the millions of nasal obstruction sufferers who currently forgo treatment. Faced with the choice between inaction and the appointments, extensive recovery period, and uncertain outcome inherent with surgery, the majority of individuals—especially those with minor to moderate obstruction—elect to live with their symptoms, which present a constant bother, source of embarrassment, and long-term health risk.

While existing nasal dilators are effective in temporarily relieving their symptoms, sufferers agree that existing products are not an option for use in their daily lives. However, these same individuals insist that a comfortable and discreet device would present a preferred solution to surgery to aid their breathing during the day. This trial will provide the clinical evidence necessary to evaluate and inform redesigns of existing prototypes to aid in the development of a finalized product ready for the market.

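### The only stated test, a conditional and unqualified ANOVA at p < 0.05, does not answer the primary objective: it names no Schnozzle contrast, analysis cohort or error-rate rule

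*Combined protocol and SAP*

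**What the plan says.** **Objective.** Section 2 sets as primary the effectiveness of Schnozzle "compared to existing nasal dilator products and a control (unaided breathing"), judged on PNIF and NOSE. Section 7a names both as primary outcomes, before the trial and with each device.

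**Design.** Under Study design (section 4a), unaided PNIF is taken first. Five marketed dilators and Schnozzle are then fitted in turn: "the order of fitting nasal dilators will be randomized", and "Each subject will undergo PNIF testing for all six devices". Section 4e adds that the baseline is taken "without any assistive devices in place, which serves as the placebo/ non-treatment arm of the study". Each person therefore supplies seven PNIF conditions.

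**Analysis.** Section 7c holds the whole plan: "If we proceed to pursue statistical evaluation of the data we will use ANOVA", at p < 0.05. The same section says "The purpose of this pilot study is to understand patient needs and preferences regarding nasal dilators". It borrows 80% power at alpha 0.05 with 30 patients from previous work. It first gives 70 people with nasal valve collapse, then 35 with and 35 without, losing 5 from each.

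**Not stated anywhere.** The plan gives no ANOVA factors, within-person term, Schnozzle contrast, follow-up test, analysis cohort, or rule for sharing the 0.05 across comparisons or between PNIF and NOSE.

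**The concern.** The objective is about one named device and two kinds of comparator. An overall F answers a different question: whether the seven condition means are all equal. A significant F does not say whether Schnozzle is among the conditions that differ, from which comparator it differs, or in which direction.

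Follow-up comparisons would be needed to reach the objective, and the plan leaves them open. Which contrasts are run, in which cohort, on which outcome and with what adjustment could all be settled after the data are seen, as could the decision to test at all. At stake is whether any p-value later attached to Schnozzle has a known error rate.

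**Working it through.** **Inputs from the documents.** Completers per cohort: 35 − 5 = 30. Conditions: 1 unaided + 5 marketed + 1 Schnozzle = 7. Schnozzle contrasts per outcome: 1 + 5 = 6. Alpha is 0.05 and cited power is 80% (section 7c).

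**The plan's own figure.** The 80% power at n = 30 cannot be reproduced, because no difference, SD or test is given. It can only be inverted. For a two-sided paired t-test with 29 df, the noncentral t gives 80% power at d = 0.529, so the noncentrality is 0.529 × √30 = 2.90. This d is an assumption and is given to every device that works.

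**What the F can tell.** The simulation used n = 30, seven conditions, equal variances and correlations, SD of paired differences fixed at 1, and 40,000 trials per main scenario. The statistic was the repeated-measures F on 6 and 6 × 29 = 174 df. Participant effects cancel, so the assumed correlation does not matter.

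| Truth | F significant |
|---|---|
| All seven equal | 5% |
| One marketed device works, Schnozzle does not | 81% |
| Only Schnozzle works | 81% |
| All five marketed devices work, Schnozzle does not | 97% |

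The second and third rows match, so the F cannot tell those two situations apart.

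**What follow-up contrasts would cost.** Six Schnozzle paired t-tests, each at unadjusted 0.05. The table gives the chance per trial of at least one false Schnozzle contrast.

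| Truth | F gate | False contrast |
|---|---|---|
| All equal | none | about 21% |
| All equal | F significant | about 4% |
| One other condition differs | F significant | about 17% |
| All five marketed devices work | F significant | about 5% |

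The gate protects when nothing differs. It also does little harm in the last row, because only Schnozzle versus unaided is then a true null. It fails in the third row: one real difference elsewhere opens the gate while five Schnozzle contrasts are still null.

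**Period adjustment.** Unaided is always measured first, so its indicator is identical to that of the first period. Intercept, condition and period over all seven measurements give 1 + 6 + 6 = 13 columns of rank 12, and Schnozzle minus unaided is not estimable. Over the six randomised device periods there are 1 + 5 + 5 = 11 columns of rank 11, and device contrasts are estimable.

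**Cost of Holm.** The six-period model has 30 × 6 − 1 − 29 − 5 − 5 = 140 residual df. At noncentrality 2.90, power for one contrast is 82% at 0.05 (critical t 1.98) and 61% at 0.05/5 = 0.01 (critical t 2.61). Simulation with random orders gave 82% and 60%.

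**Precision if no test is made.** The 95% CI half-width for a paired difference is t(0.975, 29)/√30 = 2.045/5.477 = 0.37 SD of the differences.

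**The case against.** The strongest reply is that the section says only ANOVA. It does not say that a lone overall F is the end of the analysis, and ANOVA commonly leads to contrasts. Testing is optional, the study is a pilot, no success rule hangs on p < 0.05, and section 9 presents the aim as redesign: "This trial will provide the clinical evidence necessary to evaluate and inform redesigns of existing prototypes".

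Much of this stands, and it limits the point in four ways.

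- A reader might take 81% or 97% as false-positive rates. They are not. In those scenarios devices really do differ and the F is right to say so. They would mislead only if the result were credited to Schnozzle, and the plan does not say it will be.
- A reader might take 21% as the plan's error rate. That is the ungated, all-equal case. Follow-up after a significant F is at least as natural a reading, and gives about 4%, 17% or 5% depending on the truth.
- A reader might infer a between-person ANOVA that discards the pairing. Section 4a calls the study a crossover and tests everyone with every device, so this is unlikely. Pooling the two cohorts is likewise unstated. Both are readings for the wording to rule out.
- The 0.53 comes from inverting a cited power statement and assumes a paired t-test.

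The reply does not supply the missing contrasts. Section 7c still fixes a significance threshold and justifies the sample size by power, and section 2 still sets a comparative effectiveness objective.

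**Conclusion.** The point holds as a mismatch between the objective and the one stated test. Confidence is high that no Schnozzle contrast, cohort or error-rate rule is given, and that an overall F cannot stand in for them. Neither conclusion depends on the assumed effect size.

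The magnitudes are illustrative. They rest on 30 completers with collapse, equal variances and correlations, and a paired difference of 0.53 SD. On those assumptions the F responds identically (about 81%) whether one marketed device or only Schnozzle works, and unadjusted follow-up has a familywise error between about 4% and 21%.

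The documents do not support the stronger inference that the plan will produce false claims about Schnozzle: it commits to no claim and may run no test. This should be fixed before any data are analysed, but it does not undermine the design.

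**What to change.** Choose one of two options and say which.

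**Option A, if tests are kept.** Replace the ANOVA sentence in section 7c with wording to this effect:

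> PNIF is analysed within person in the nasal valve collapse cohort. Schnozzle minus unaided is estimated as a paired difference with 95% CI and tested at two-sided 0.05. Only if this is significant is Schnozzle compared with each of the five marketed dilators, in a mixed model on the six randomised clinic device periods (device and period fixed, participant random), with Holm adjustment. NOSE, and the cohort without collapse, are reported as within-person differences with 95% CIs and no significance claim.

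Keep the unaided measurement out of the period model. State that it always comes first, so the contrast with unaided is not protected from order effects.

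**Option B, equally acceptable for a pilot.** Delete the ANOVA and the p < 0.05 threshold, declare the study descriptive, and report the same Schnozzle differences with 95% CIs.

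**Cost.** Protocol wording only, with no extra visits or measurements. Under A, a device-versus-device contrast with about 82% power unadjusted has about 61% at the strictest Holm step, and the gate lowers that further. NOSE also loses any significance claim. Under B there are no significance claims at all, and each paired difference carries a CI half-width of 0.37 SD of the differences at n = 30.
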